6.0 LIST OF ABBREVIATIONS

Abbreviation	Term
ADE	adverse device effect
AE	adverse event
ANOVA	analysis of variance
BSCVA	best spectacle-corrected visual acuity
CFR	Code of Federal Regulations
eCRF	electronic Case Report Form
D	diopter
FDA	US Food and Drug Administration
GCP	Good Clinical Practice
HIPAA	Health Insurance Portability Accountability Act
ICF	Informed Consent Form
ICH	International Conference on Harmonisation
ID	identification
IRB	Institutional Review Board
ISO	International Organization for Standardization
ITT	intent-to-treat
logMAR	logarithm of the minimum angle of resolution
MCMC	Markov chain Monte Carlo
MedDRA	Medical Dictionary for Regulatory Activities
MPS	multi-purpose solution
OD	Doctor of Optometry
PP	per-protocol
SAE	serious adverse event
SAP	Statistical Analysis Plan
SD	standard deviation
UADE	unanticipated adverse device effect
US	United States
USAN	United States Adapted Name
VA	visual acuity

NOTE: The first occurrence of some abbreviations is not spelled out in the document (eg, units of measure).

7.0 INTRODUCTION

Bausch + Lomb is evaluating the safety, efficacy, and product performance of an investigational silicone hydrogel contact lens. Silicone hydrogel contact lenses offer the advantage of high oxygen transmissibility compared to non-silicone hydrogel soft contact lenses, promoting the level of health of the eye.

8.0 OBJECTIVE

The objective of this study is to evaluate the safety and efficacy of a custom silicone hydrogel contact lens when worn on a daily basis by currently adapted soft contact lens wearers.

9.0 STUDY DESIGN

9.1 Description of Study Design

This is a multicenter, randomized 2:1, parallel, bilateral, double-masked study at 7 to 10 investigative sites in the United States (US) comparing the Bausch + Lomb custom samfilcon B (test) lens with the hioxifilcon D, 54% water, Alden Optical® HP Sphere (control) lens.

Approximately 84 subjects will be enrolled in this 3-month study.

At the Screening Visit, approximately two-thirds of the eligible subjects will be randomized to receive the test lens (custom samfilcon B lenses) and the other one-third eligible subjects will be randomized to receive the control lens (Alden Optical HP Sphere). Both groups will wear their assigned lenses on a daily wear basis throughout the study with visits planned for Screening (Visit 1), Dispensing (Visit 2), 1 Week (Visit 3), 1 Month (Visit 4), 2 Months (Visit 5), 3 Months (Visit 6) and/or a final Exit Visit.

Subjects will be randomized sequentially by the randomization system as they are enrolled. Subjects will be dispensed product according to their assigned treatment and will remain masked during the entire study period.

Subjects will be provided with test or control lenses as part of the dispensing package along with instructions for the use and care of the lenses.

Subjects will be provided with ReNu MultiPlus® Lubricating and Rewetting Drops for use as needed during the study.

Subjects will store their worn study lenses in a lens case filled with Bausch + Lomb Biotrue[®] multi-purpose solution (MPS).

9.2 Selection of Study Population

Written informed consent, enrollment in the study, or dispensing of study products cannot begin until the Investigator has received Institutional Review Board (IRB) approval to conduct the study. The Sponsor and IRB must approve any advertising used to recruit subjects prior to use of that advertising.

All consented subjects must be accounted for, whether they participate in the study or not. Bausch + Lomb will provide a Screening Log on which to enter information for each

subject who signs an Informed Consent Form (ICF). All screened subjects must be entered onto the Screening Log, in the order in which they were consented, where they will be assigned a sequential subject identification (ID) number. Once a potential subject is consented and their initials are entered onto the Screening Log, the Investigator should proceed with Screening procedures.

Potential subjects are deemed either "Screen Pass" or "Screen Fail." "Screen Fail" subjects are subjects who have not met the study inclusion criteria or have met the exclusion criteria and cannot be randomized into the study.

"Screen Pass" subjects have met all of the study inclusion criteria and have not met any of the exclusion criteria. Only "Screen Pass" subjects can be randomized to receive the study lenses and can be assigned a subject identification (ID) number from the randomization system.

Once a subject is randomized, a subject is considered active and must be accounted for at every visit until exited (completed or discontinued) from the study, even if they are not dispensed study materials. Refer to Section 9.2.4 for subjects determined to be lost to follow-up.

9.2.1 Eligibility

9.2.1.1 Inclusion Criteria

- 1. Subjects must be 18 to 40 years old on the date the ICF is signed and have the capacity to provide voluntary informed consent.
- 2. Subjects must be able to read, understand, and provide written informed consent on the IRB-approved ICF and provide authorization as appropriate for local privacy regulations.
- 3. Subjects must have clear central corneas and be free of any anterior segment disorders in each eye.
- 4. Subjects must be myopic, require contact lens correction from -1.00 diopter (D) to -6.00 D, and wear contact lenses in each eye.
- 5. Subjects must be correctable through spherocylindrical refraction to 47 letters (0.0 logarithm of the minimum angle of resolution [logMAR]) or better (distance, high-contrast) in each eye.
- 6. Subjects must be able and willing to comply with all treatment and follow-up/study procedures.
- 7. Subjects must be adapted soft contact lens wearers and agree to wear their study lenses on a daily wear basis for approximately 3 months.

9.2.1.2 Exclusion Criteria

- 1. Subjects participating in any drug or device clinical investigation within 2 weeks prior to entry into this study and/or during the period of study participation.
- 2. Subjects who are women of childbearing potential (those who are not surgically sterilized or postmenopausal) are excluded from participation in the investigation if they meet any one of the following conditions:

- She is currently pregnant.
- She plans to become pregnant during the study.
- She is breastfeeding.
- 3. Subjects who have worn gas permeable lenses in either eye within the last 30 days or who have worn polymethylmethacrylate lenses in either eye within the last 3 months.
- 4. Subjects with any systemic disease currently affecting ocular health or which in the Investigator's opinion may have an effect on ocular health in either eye during the course of the study.
- 5. Subjects using any systemic or topical medications that will, in the Investigator's opinion, affect ocular physiology or lens performance.
- 6. Subjects with an active ocular disease in either eye or who are using any ocular medication.
- 7. Subjects who currently wear monovision, multifocal, or toric contact lenses in either eye.
- 8. Subjects with an ocular astigmatism >1.00 D in either eye.
- 9. Subjects with anisometropia (spherical equivalent) >2.00 D.
- 10. Subjects with any Grade ≥2 finding in either eye during the slit lamp examination (refer to APPENDIX B for methods of clinical evaluation). Subjects with corneal infiltrates in either eye, of ANY GRADE, are not eligible to participate in this study.
- 11. Subjects with any "Present" finding during the slit lamp examination in either eye (refer to APPENDIX B for methods of clinical evaluation) that, in the Investigator's judgment, interferes with contact lens wear.
- 12. Subjects with any scar or neovascularization within the central 6 mm of the cornea in either eye. Subjects with minor peripheral corneal scarring (that does not extend into the central area), that in the Investigator's judgment, does not interfere with contact lens wear, are eligible to participate in this study.
- 13. Subjects who are aphakic in either eye.
- 14. Subjects who are amblyopic in either eye.
- 15. Subjects who have had any corneal surgery (eg, refractive surgery) in either eye.
- 16. Subjects who are allergic to any component in the study care products.
- 17. Subjects who meet any of the following criteria:
 - The subject is an employee of the investigative site.
 - The subject, or a member of the subject's household, is an ophthalmologist, an optometrist, an optician, or an ophthalmic assistant/technician.
 - The subject, or a member of the subject's household, is an employee of a manufacturer of contact lenses or contact lens care products (eg, Alcon, Bausch + Lomb, Ciba Vision, CooperVision, Johnson & Johnson, etc.)
 - The subject, or a member of the subject's household, is an employee of a market research firm.

If a subject meets all the inclusion criteria and does not exhibit any of the exclusion criteria, the subject is eligible for entry into the study. Ineligible subjects MUST NOT be enrolled in this study and are considered a "Screen Fail". Any subject enrolled in the study who later is found to have not met the eligibility criteria at entry will be discontinued.

9.2.2 Subject Completion

The subject has completed the study when the 3-Month Visit is concluded. Subjects who require further follow-up will be followed according to the Adverse Event or Unscheduled Visit Section.

9.2.3 Subject Discontinuation

A subject MAY be discontinued (at the discretion of the Investigator, the Sponsor, and/or the IRB) prior to the final study visit for a variety of reasons, including, but not limited to:

- An adverse event (AE) occurring during the course of the study, which precludes continued treatment or follow-up
- Persistent Grade 3 or 4 slit lamp findings (must be reported to the Sponsor within 24 hours)
- Persistent study-related symptoms/complaints

A subject MUST be discontinued prior to the final study visit (3-Month Visit [Visit 6]) for any of the following reasons:

- Voluntary withdrawal
- Death
- Investigator decision that it is not in the best medical interest of the subject to continue participation in the investigation
- Ineligible after randomization a subject who was enrolled but was later found to have not met the eligibility criteria in the protocol
- Inability to maintain recommended wearing schedule
- Continued failure to follow subject instructions
- Misses more than one consecutive follow-up visit
- Lack of motivation
- Lost to follow-up (refer to Section 9.2.4)
- Instillation of non-medically indicated solution not specified in the protocol
- Other eye is discontinued
- Becomes pregnant during the study

Prior to discontinuing a subject, every effort should be made to contact the subject, schedule an Exit Visit, obtain as much follow-up data as possible, and retrieve all study materials. Adverse events will be followed as described in Section 13.0. Subject

discontinuations will be documented clearly on the source document and applicable eCRF. The Investigator should indicate the PRIMARY (one) reason that the subject was discontinued for each eye. Subjects who are discontinued from the study following randomization will not be replaced.

Exit Visit assessments should be completed for discontinued subjects.

9.2.4 Lost to Follow-Up

Subjects who do not return for scheduled follow-up visits, as defined by the visit window and cannot be contacted, are to be considered lost to follow-up. All attempts to contact the subject should be documented and kept with the subject's source documentation, and the applicable eCRFs will be completed. The exit date will be the date of the subject's last visit to the clinic as a study subject.

9.3 Investigators

The study will be conducted at approximately 7-10 investigative sites located in the US by Investigators who are determined by Bausch + Lomb to be suitably qualified by training and experience to conduct this study. Principal Investigators and Sub-Investigators will be identified on the Device Investigator Agreement Form.

Each Investigator will attempt to enroll approximately 8-12 subjects. In the event that selected sites do not meet full enrollment, the Sponsor may decide to increase enrollment as needed at other currently active sites and/or additional site(s) may be added to satisfy the enrollment requirements of the study.

9.4 Study Duration

Subjects will be followed for 3 months after dispensing (unless discontinued or lost to follow-up) and must adhere to the following schedule:

Table 1. Schedule of Visits

Visit Number	Visit Name	Target	Acceptable Visit Range
1	Screening Visit	None	Day -30 to Day-7
2	Dispensing Visit	Day 1	Not applicable
3	1-Week Visit	Day 8	Day 5 – 9
4	1-Month Visit	Day 31	Day 27 – 35
5	2-Month Visit	Day 61	Day 54 – 68
6	3-Month Visit	Day 92	Day 91* – 101

^{*}CRITICAL NOTE: The 3-Month Visit must occur no earlier than Day 91.

The visit range is based on the date test lenses are initially dispensed (Dispensing Visit). A visit scheduling table will be provided in the initial study shipment to aid the Investigator in scheduling follow-up visits.

9.5 Treatments

Approximately 56 subjects (112 eyes) will be randomized to receive Bausch + Lomb investigational custom samfilcon B lenses and approximately 28 subjects (56 eyes) will be randomized to receive Alden Optical HP Sphere contact lenses. Subjects will be assigned randomization numbers, according to the randomization system.

Subjects will wear their lenses on a daily wear basis for 3 months.

NOTE: Use of other contact lenses is not allowed during the study.

10.0 STUDY MATERIALS

Bausch + Lomb will provide all study materials at no charge to the Investigator. All study materials will be provided to the site for each subject prior to the start of the study. Refer to Section 10.8 for ordering replacement test or control product in the case of loss or damage.

10.1 Description of Test Article

The Bausch + Lomb investigational custom samfilcon B contact lens (test) is an investigational silicone hydrogel contact lens which will be provided in the following parameters:

• Sphere Power: -1.00 to -6.00 D in steps of 0.25 D

Diameter: 14.2 mmBase Curve: 8.6 mm

• Material: samfilcon B, 41% water

10.2 Description of Comparator Product

The Alden Optical HP Sphere contact lens (control) is a hydrogel contact lens which will be provided in the following parameters:

• Sphere Power: -1.00 to -6.00 D in steps of 0.25 D

• Diameter: 14.2 mm Visibility tint

• Base Curve: 8.3 mm

• Material: hioxifilcon D, 54% water

10.3 Instructions for Use and Administration

New study lenses will be dispensed at the Dispensing Visit. Lenses will be worn on a daily basis for 3 months. Subjects must wear their study lenses to all follow-up visits.

10.3.1 Storage Requirements

All test and control lenses provided by the Sponsor must be stored in a secure location accessible only to study personnel and maintained at room temperature.

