10.6 Accountability

The unmasked designee will be responsible for keeping current and accurate records of the amount of study test lenses received and dispensed, and its disposition. The study lenses must be stored under the appropriate conditions in a secure area and are to be dispensed only to subjects enrolled in the study, in accordance with the conditions specified in this protocol. During the course of the study, the unmasked designee must maintain an inventory of all lenses dispensed to or returned by the subject, including subject identifiers. A Product Accountability Log will be provided to the sites to maintain records of the study lenses assigned to each enrolled subject.

At time points throughout the study and/or upon completion of the study, the Sponsor/Sponsor's representative will review and verify the Investigator's Product Accountability Logs. Following verification, and as directed by the Sponsor, all worn and unworn lenses must be returned to the Clinical Trial Materials Supply Management at the address listed on the Personnel and Facilities page.

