10.7 Masking/Unmasking

This study is double-masked; therefore, the Investigator/site staff, subjects, and Bausch + Lomb personnel or designee(s) involved in the collection of study data will be masked to the study lenses. Each site must have an unmasked designee that will be responsible for dispensing and accountability. This designee shall not participate in study assessments that may cause bias to the study data. Study Monitors will become unmasked during site visits when they perform product accountability.

Lens markings on both products are not product-specific. Markings and lens tints are similar between products and are indistinguishable.

Randomization will be produced prior to study enrollment by an unmasked statistician not otherwise involved in the trial. An unmasked designee will be responsible for dispensing the test and control lenses according to the randomization system. Investigators will not have access to the randomization system information and lenses will be dispensed directly to the subject, thereby maintaining Investigator masking. In an effort to ensure that both the Investigator and subject remain masked, the unmasked designee MUST dispense the study lenses and MUST remove lenses from their glass vials out of the Investigator's and subject's sight immediately prior to dispensing. Subjects will not be given additional replacement lenses to take home, thereby

maintaining subject masking. A reserve pair will remain at the site if a replacement is needed.

The Investigator should contact the Medical Monitor prior to unmasking of study lenses. In an emergency situation, however, where knowledge of the study lenses is critical to subject safety, the code may be broken by requesting the allocated treatment for that subject from the unmasked designee.

The Investigator must notify the Sponsor as soon as possible after unmasking. In addition, the Investigator must record the date, time, and reason for unmasking the study treatment in the source documentation.

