10.8 Replacement Lenses

Replacements are permitted for damage, satisfaction, and vision at the discretion of the Principal Investigator. All lens replacements need to be tracked for reason and date and must also be rechecked for fit.

A reserve pair of study lenses for each dispensed subject should be retained in-office at all times in case a non-scheduled lens replacement is required. If the reserve is used, an immediate replacement order is required. Any additional/replacement of test or control products (in the case of loss or damage) must be ordered through Clinical Trial Materials using the Replacement Lens Order Form for Study #886. Do not order through Bausch + Lomb Customer Service. The form can be scanned to

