 - Only "Screen Pass" subjects should be randomized in the study.
- g. If the subject is eligible, collect Symptoms/Complaints and Subjective Assessment information from the subject regarding their habitual lenses.
- h. Assign subject numbers based on the randomization system. The unmasked designee will determine the subject's randomized lens by using the randomization system and record on the Screening Log.
- i. Assess BSCVA to determine subject prescription. The prescription determined from this fitting assessment will be used to dispense/order test or control lenses according to the lens to which the subject is randomized.
- j. Record the lens parameters to be dispensed/ordered based on the diagnostic fitting.
- k. For each subject, use the lens order form to order the appropriate study contact lenses (test or control). Schedule the subject for their Dispensing Visit within 30 days.

- 1. Collect/assess all AEs, including serious or significant non-serious AEs, since consent was signed.
- m. For female subjects, re-emphasize the exclusion criterion stating that if the subject is of childbearing potential and is pregnant and or breast feeding, she is ineligible to be a part of the study.

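### Lens storage and reserve pairs are open to masked study staff, although the vial labels identify the arm

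*Combined protocol and SAP*

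**What the plan says.** All places are in the combined protocol and SAP.

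- **Who is masked (10.7).** The study is double-masked: "the Investigator/site staff, subjects, and Bausch + Lomb personnel or designee(s) involved in the collection of study data will be masked to the study lenses".
- **What the unmasked designee does (10.6, 10.7).** "Each site must have an unmasked designee that will be responsible for dispensing and accountability". On records, "The unmasked designee will be responsible for keeping current and accurate records of the amount of study test lenses received and dispensed". At dispensing, the designee "MUST remove lenses from their glass vials out of the Investigator's and subject's sight immediately prior to dispensing".
- **Who may reach the stored lenses (10.3.1).** Lenses "must be stored in a secure location accessible only to study personnel and maintained at room temperature". Section 10.6 adds only that the area be secure.
- **What the label shows (10.5).** Both labels list base curve and manufacturer. Only the test vial is described as carrying an investigational label, and only its list includes a caution statement.
- **What separates the products (10.1, 10.2).** Each has a single base curve: 8.6 mm for test and, for control, "Base Curve: 8.3 mm". Diameter (14.2 mm) and power range are the same.
- **Where vials are kept during follow-up (10.8).** "A reserve pair of study lenses for each dispensed subject should be retained in-office at all times".
- **Ordering (12.1.1, 10.8).** Step h of screening names the unmasked designee. Step k says to "use the lens order form to order the appropriate study contact lenses (test or control" and names no one. The Replacement Lens Order Form in 10.8 also has no named owner.

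**The concern.** The masking rules treat the vial as something that gives the arm away: the designee must open it where neither the Investigator nor the subject can see, and monitors are said to become unmasked when they check accountability. That protection covers the moment of dispensing. The storage rule covers the rest of the study, and it admits all study personnel.

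Masked staff assess both primary outcomes. High-contrast lens acuity is measured at five scheduled visits. Slit lamp findings are graded at every follow-up visit, and an eye counts as an event above Grade 2. Both can be moved, without intent, by an assessor who knows the lens. A shift that favours the test lens makes a non-inferiority conclusion easier to reach, and no later analysis can remove it.

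**Working it through.** **1. Reading the sections together**

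1. Section 10.7 requires the Investigator and data-collecting staff to be masked. Section 10.3.1 lets study personnel, without distinction, reach the lenses. A masked examiner who follows 10.3.1 is within the rules when handling stock.
2. The label lists base curve (10.5). With one base curve per product, 8.6 mm or 8.3 mm identifies the product. Manufacturer and the test-only caution statement are further cues.
3. The listed label items include no subject identifier, so seeing a vial does not by itself unmask a subject. A link can come from the reserve pair, which is held for each dispensed subject (10.8).
4. Where the protocol wants a task confined to the designee, it says so: randomization (10.10.2, 12.1.1 step h), dispensing (10.7, 12.1.2), replacement dispensing (12.1.5.1) and records (10.6). It does not say so for storage access, reserve pairs or either order form.

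**2. The plan's own figures**

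Inputs: 100 test and 50 control eyes, SD 0.076, margin 0.06, one-sided 0.05 (14.4.1); 0.012 in both arms, margin 0.10 (14.4.2).

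- Acuity: SE = 0.076 × √(1/100 + 1/50) = 0.0132. Noncentral t, 148 df, noncentrality 0.06/0.0132 = 4.56: power 0.998 (plan: 99%).
- Safety: exact enumeration of the Newcombe-Wilson upper limit below 0.10 gives 0.999 (plan: 99%).

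Both agree with the plan, and this point disputes neither.

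**3. Sensitivity to an assumed bias, acuity**

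Three letters are 0.06 logMAR (14.1.1), so one letter is 0.06/3 = 0.02, and 0.02/0.06 = one third of the margin. If the true difference is exactly 0.06 and assessment shifts the result by b in favour of test, false success = P(t > 1.655 | noncentrality b/SE):

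| Assumed b (logMAR) | Letters | b/SE | False success |
|---|---|---|---|
| 0 | 0 | 0 | 5% |
| 0.01 | 0.5 | 0.76 | 19% |
| 0.02 | 1 | 1.52 | 45% |
| 0.03 | 1.5 | 2.28 | 73% |

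Eyes are treated as independent, as the plan does (14.7.1.1). Because the endpoint averages five visits, b must be a shift sustained across them.

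**4. Sensitivity near the boundary, safety**

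With no control events, the Newcombe-Wilson upper limit equals the Wilson upper limit for test: [p + z²/2n + z√(p(1−p)/n + z²/4n²)] / (1 + z²/n), with z = 1.645 and n = 100.

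- 6/100 v 0/50: (0.06 + 0.0135 + 0.0413)/1.0271 = 0.112, fail.
- 5/100 v 0/50: (0.05 + 0.0135 + 0.0383)/1.0271 = 0.099, pass.
- 6/100 v 1/50: 0.04 + √(0.0518² + 0.0155²) = 0.094, pass.

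One re-graded test eye decides the first pair, but the pair was chosen to straddle the margin. At the planned 0.012, the chance of six or more events among 100 independent eyes is about 0.1%.

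**The case against.** **Storage is implied.** The designee holds accountability, the secure-storage sentence in 10.6 sits among the designee's duties, and the masking rule in 10.7 should govern who counts as study personnel. A careful site may well read it that way. But 10.3.1 states the wider rule in terms, and no section narrows it.

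**Ordering is already with the designee.** This largely stands. Investigators have no access to the randomization information (10.7), the designee obtains the assignment (10.10.2, 12.1.1 step h), and nobody without it can order test or control lenses. Step k lacks a role name, not a safeguard. A reader might infer that step j has the masked Investigator write down an identifying base curve. The text does not require it: base curve and diameter are fixed by product, so power is all that the refraction settles, and the dispensing records in 12.1.2 and 12.1.5.1 ask for power only.

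**Stronger readings to avoid.** A reader might infer that all 84 subjects will be unmasked. That is possible exposure: the text permits access, and the listed label carries no subject identifier. A reader might also take the safety example as a forecast; it lies far from the planned rate. Nothing supplied describes how letters are prompted, so a one-letter effect is an assumption.

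**Unseen material.** The order forms and the appendices after A are not in the supplied text and could restrict access. If they do, 10.3.1 should agree with them.

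**A more direct route exists.** The designee records the randomized lens on the Screening Log (12.1.1 step h), which the Investigator signs and keeps. That needs its own correction, which would still leave labelled vials within reach.

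**Conclusion.** The gap is real but limited. As written, 10.3.1 allows masked assessors of both primary outcomes to reach vials whose labels identify the product, and 10.8 keeps such vials on site for each dispensed subject. This conflicts with the purpose of 10.7. The order forms are a matter of naming the role.

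The documents do not show that unmasking will occur, and they give no basis for estimating a bias. The scale rests on assumption: a sustained one-letter shift favouring test is a third of the acuity margin and, at a true difference of 0.06, would raise false success from 5% to about 45% (19% to 73% for 0.5 to 1.5 letters). The safety counts show only that one eye can matter near the boundary. The point is worth acting on because prevention costs almost nothing. It is a cheap improvement, not a fault that invalidates the design.

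**What to change.** - **10.3.1:** limit access to stored test and control lenses to the unmasked designee, in place of study personnel generally.
- **10.8:** state that reserve pairs are held under the same restriction, and that the unmasked designee completes and files the Replacement Lens Order Form.
- **12.1.1 step k:** name the unmasked designee as the person who completes and files the lens order form, consistent with step h and 10.7. State that masked staff supply sphere power only.
- Check that the order forms and the remaining appendices say the same.

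Cost: wording and site training. Each site must already have an unmasked designee (10.7), and that person must already dispense any replacement (12.1.5.1). Sample size, visits, endpoints and analysis do not change.
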